Rationale: Although we considered an attention-matched condition to control for nonspecific intervention effects, we decided against this approach because medication monitoring is likely to improve adherence alone.⁵² Additionally, requesting participation in a placebo intervention adds undue burden to BCS who are coping with emotional and physical sequelae. Finally, an attention control should only be employed if attention would affect the primary outcome. Since no data suggest that attention would improve AET adherence, an attention control would be an added expense and unethical.⁵² Finally, participants who identify as part of a racial/ethnic minority population will be offered the opportunity to participate in a qualitative exit interview to provide feedback on the STRIDE study.

Retention. Strategies to promote retention will include accurate explanations of study expectations during the recruitment process,⁵³ collection of locator information and a secondary contact (Appendix 3.12), a phone check-in to ensure use of MEMS Caps, branding of study materials for project identity, and reimbursement for time (\$20/assessment). Intervention participants will receive a text reminder one day prior to the scheduled ZOOM session (See Section 5.2 detailing Participant Communication).

9.3 *Study Instruments*

The following questionnaires have been specifically selected to reflect the theoretical intervention targets and aims of the study. All participants will complete the baseline questionnaires within four weeks of documented informed consent. If a participant does not complete the baseline questionnaires within this timeframe, she will be re-screened and re-consented, restarting the four-week window. Follow-up assessments will be completed at 12-week (+/- 2 weeks) and 24-week (+/- 2 weeks) from time of baseline completion (Appendix 30.16) Table 3 details the schedule for administering all study instruments. Patient assessments can be found in Appendix 30.16. We anticipate that 15-20% of 12-week assessments will be out

of window for intervention participants, given the occasional delay of coordinating multiple patients' schedules to arrange the intervention groups.

Instrument/Measure:	Screening	Baseline (4-week window from consent)	12-weeks post-baseline (+/- 2-week window)	*24-weeks post-baseline (+/- 2-week window)
Chart review	X			
Adapted NCCN Distress Thermometer	X			

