Medication Event Monitoring System (MEMS Caps)		To be used throughout the 24-week study period		
Demographics		X		
Medication Adherence Report Scale (MARS-5)		X	X	X
Breast Cancer Prevention Trial Symptom Checklist (BCPT)		X	X	X
Cancer Therapy Satisfaction Questionnaire (CTSQ)		X	X	X
Hospital Anxiety and Depression Scale (HADS)		X	X	X
Functional Assessment of Cancer Therapy (FACT-B)		X	X	X
Measure of Current Status (MOCS)		X	X	X
Beliefs About Medications Questionnaire – Adjuvant Endocrine Therapy (BMQ-AET)		X	X	X
Multidimensional Scale of Perceived Social Support (MSPSS)		X	X	X
Self-Efficacy in Appropriate Medication Use Scale (SEAMS)		X	X	X
Self-Efficacy For Managing Symptoms and Taking AET Questionnaire (Self-Efficacy For Symptoms)		X	X	X
Patient-Reported Outcomes Measurement Information System (PROMIS) – Cognitive Function – Short Form 4a		X	X	X
Client Satisfaction Questionnaire (CSQ)**			X	
Supplemental Medication Diary	To serve as optional as-needed supplement to MEMS Caps (e.g., on vacation)			
Session Rating Form	To be administered during the run-in period after each intervention session			
Intervention Acceptability Form	To be administered during the run-in period at 3-months post-baseline			
Semi-structured Exit Interview	To be conducted during the run-in period at 3-months post-baseline			
Semi-structured Exit Interview	To be conducting during the RCT period after participants complete their participation in the STRIDE program.			

*Run-in participants will not complete a 24-week assessment

**CSQ will be administered to intervention participants only

Screening:

Adapted National Comprehensive Cancer Network (NCCN) Distress Thermometer (Included as part of Study Screening Script in Appendix 30.3 and independently in Appendix 30.17): The NCCN Distress Thermometer is a valid, one-item measure for assessing distress in many cancer populations.⁵⁴ This

measure is scored on a range of 0 (no distress at all) to 10 (extremely distressed), and a score of 4 has been identified as an appropriate cut-off to measure significant distress.⁵⁵ This measure has been modified in this study for the purpose of screening BCS for distress related to taking AET, distress related to breast cancer symptoms/side effects, and distress related to adherence to AET. Participants who indicate a score of ≥ 4 on any of the three distress thermometers will be eligible for participation.

Secondary Outcomes:

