Hypothesis 1. We hypothesize that participation in the STRIDE intervention will be associated with an increase in adherence and satisfaction with AET and a decrease in symptom distress at 12-weeks compared to the medication monitoring control, and that these improvements will maintain at 24-week follow-up.

Data will be assessed for patterns of missingness⁷² and statistical assumptions. We will conduct mixed effects models with repeated measures data and relevant covariates such social support (MSPSS) and demographic and treatment-related factors (e.g., age, stage, time since AET initiation) as potential covariates. Longitudinal analyses will include all time points and a cross-sectional analysis for each time point. Given that this pilot is not powered to detect statistically significant group differences, we will examine mean differences and sample variability. Effect sizes (Cohen's d) will be calculated for changes in outcomes from baseline to four and eight months, as (Mean change score [intervention arm] – Mean change score [control arm])/SD pooled, where 0.3 indicates a small effect, 0.5 a medium effect, and 0.8 a large effect.⁷³ Effect sizes will be used in a power analysis to estimate the necessary sample size to conduct a full-scale efficacy trial with power >80%. We will also verify the needed sample size based on ability to detect a clinically meaningful difference and references to existing literature.⁷⁴

Exploratory Aim. To assess the effects of the STRIDE intervention on several psychosocial constructs, exploring potential mediator and moderators of the intervention.

Exploratory Hypothesis: We will explore whether participation in the STRIDE intervention is associated with an increase in QOL and medication-taking self-efficacy, and a decrease in distress (anxiety and depression at 12-weeks compared to the medication monitoring control, and whether these improvements are maintained at 24-week follow-up.

We will use the same procedure to assess changes in secondary outcomes in the intervention group. We will explore potential mediation of secondary and exploratory endpoints through changes in beliefs about adjuvant endocrine therapy (BMQ-AET) and/or perceived coping skills (MOCS), as well as self-efficacy for managing symptoms (Self-Efficacy For Symptoms).

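### Section 11.1 sets Cohen's d at four and eight months, which the 12- and 24-week schedule cannot supply, and does not link d to the planned mixed model

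*Combined protocol and SAP*

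**What the plan says.** Section 11.1 (Secondary Aim) states that Cohen's d "will be calculated for changes in outcomes from baseline to four and eight months". The hypothesis in the same text expects benefit "at 12-weeks compared to the medication monitoring control, and that these improvements will maintain at 24-week follow-up".

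The schedule is set elsewhere:
- Section 9.3: "Follow-up assessments will be completed at 12-week (+/- 2 weeks) and 24-week (+/- 2 weeks) from time of baseline completion".
- The schedule table in Section 9.3 lists the MEMS caps as "To be used throughout the 24-week study period", and Section 9.3 plans weekly and monthly adherence scores.
- Section 7.0 puts each participant's enrolment at about 24 weeks.
- Section 8.2 places the questionnaire endpoints at 12 and 24 weeks and compares MEMS adherence over the whole 24 weeks. Section 8.3 labels the exploratory time points 10 and 24 weeks.

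On the calculation, the formula subtracts raw mean changes and ends "Mean change score [control arm])/SD pooled". Mixed models are planned with "relevant covariates such social support (MSPSS) and demographic and treatment-related factors", and "Longitudinal analyses will include all time points and a cross-sectional analysis for each time point". Randomisation is stratified by HADS distress (Section 9.1). Section 11.1 then says "Effect sizes will be used in a power analysis to estimate the necessary sample size" for a full-scale trial, and also plans to verify that size against a clinically meaningful difference and the literature. Section 11.2 refers both to a focus on completers and to intention-to-treat with imputation.

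**The concern.** The effect sizes are one of the pilot's stated products, because they inform the size of the next trial. The rule that defines them names two times at which no questionnaire is scheduled, one of them after all data collection has ended. An analyst following the text literally could not carry it out.

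The same sentence also separates d from the model the plan intends to fit. A raw change-score difference ignores the baseline adjustment that the collected data would support. The factor used to stratify randomisation is not among the covariates named. If d is computed only in participants who return both questionnaires, it also loses whatever protection against informative dropout the model would give. Finally, the formula does not say which SD is pooled, and a later reader needs that to turn d into a sample size.

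**Working it through.** The documents give no sample size, power or alpha for the secondary effect sizes, so there is no stated figure to reproduce.

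**Time points.** One month is 365.25/12/7 = 4.348 weeks.
- Four months: 4 × 4.348 = week 17.4. Eight months: 8 × 4.348 = week 34.8.
- Windows from Section 9.3: 12 ± 2 gives weeks 10 to 14; 24 ± 2 gives weeks 22 to 26.
- Week 17.4 is 17.4 − 14 = 3.4 weeks after the first window closes and 22 − 17.4 = 4.6 weeks before the second opens.
- Week 34.8 is 34.8 − 26 = 8.8 weeks after the last window closes.
- MEMS runs to week 24, so a four-month adherence score would exist and an eight-month one would not.
- The phone check-ins at months four and five (Section 9.2) belong to the intervention; the schedule attaches no questionnaire to them. Section 9.3 expects 15–20% of the intervention arm's 12-week assessments to be out of window. A few could fall near week 17, but that is not a four-month assessment in both arms.
- The preliminary-studies text in Section 2.0 records that the study was shortened from eight months to six, which is the likely origin of the phrase.

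**Precision.** Inputs: 100 randomised (Section 4.0) and 80% retention anticipated (Section 11.1), hence 80 completers, 40 per arm. Assumed: outcome SD 1 at each time, equal correlation r between times, and complete data in those 80. The documents give no r, so 0.3 to 0.7 is shown.
- Change-score variance of the arm difference: (4/80) × 2(1 − r). A mixed model with baseline free in each arm gives the same value.
- Baseline-adjusted, or common baseline mean in both arms: (4/80) × (1 − r²).
- Ratio: (1 − r²)/[2(1 − r)] = (1 + r)/2.
- 95% CI half-width: 1.96 × √variance, in SD units.

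| r | Change-score variance | Half-width | Adjusted variance | Half-width | Ratio |
|---|---|---|---|---|---|
| 0.3 | 0.070 | 0.52 | 0.0455 | 0.42 | 0.65 |
| 0.5 | 0.050 | 0.44 | 0.0375 | 0.38 | 0.75 |
| 0.7 | 0.030 | 0.34 | 0.0255 | 0.31 | 0.85 |

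The further gain from adding the HADS stratum cannot be quantified from the documents.

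**The unnamed SD.** Take one true difference of 0.30 scale SD, 80% power and two-sided 5% (all assumed). Then n per arm = 2 × [SD × (1.960 + 0.842)/0.30]², rounded up.

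| SD used | r = 0.3 | r = 0.5 | r = 0.7 |
|---|---|---|---|
| Scale SD, 1 | 175 | 175 | 175 |
| SD of change, √[2(1 − r)] | 245 | 175 | 105 |
| Baseline-adjusted SD, √(1 − r²) | 159 | 131 | 89 |

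Each figure is right for the analysis that uses that SD. An error arises only if the d from one row is used to size a trial analysed as in another.

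**The case against.** The time-point slip is easy to resolve. The hypothesis in the same section, Section 8.2, the schedule and Section 7.0 all point to 12 and 24 weeks. This stands as a reason to treat it as a text correction; it does not make the current sentence executable.

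A change-score d is a legitimate descriptive summary in a pilot that disclaims power for group differences, and the covariate list is open-ended. The planned model may therefore already include the stratum and handle baseline well. That is fair, and in that case the model gains nothing in precision. But d is not said to come from that model, so the link still needs stating.

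The pooled SD of change is the natural reading when the numerator is a difference in change, and the planned check against a clinically meaningful difference limits the harm. Both stand, so naming the SD is a clarification.

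Some stronger readings are tempting but not supported:
- *No outcome exists between 12 and 24 weeks.* MEMS is recorded throughout, with weekly and monthly scores.
- *The 10-week label in Section 8.3 is equally unworkable.* Week 10 lies inside the 12-week window, so this is only an inconsistent label.
- *The change-score d is safely unbiased, or certainly biased.* With about 20% attrition anticipated and Section 11.2 naming both completers and all randomised participants, it can be biased if computed in completers and dropout is informative. The documents settle neither condition.
- *The next trial will be mis-sized by the spread from 89 to 245 per arm.* That spread rests on assumed inputs and mostly reflects different analyses.

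**Conclusion.** The time-point rule in Section 11.1 is wrong as written: no outcome can supply d at eight months, and no questionnaire is scheduled to supply it at four. This follows from the documents alone. That the phrase is left over from an eight-month design is an inference, well supported by Section 2.0.

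The link between d and the mixed model is a worthwhile improvement at almost no cost. Its size depends on the assumed r and on how the planned model treats baseline: a variance ratio of 0.65 to 0.85 against raw change scores, or no gain if baseline is already adjusted for or constrained. The protection against informative dropout is a further reason, which the documents do not allow to be quantified.

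The unnamed SD and the undesignated MEMS baseline are missing detail. The bottle is sent before randomisation (Appendix 30.29), so a pre-randomisation adherence value may exist. A reader might infer that the pilot's main result is at risk. It is not: the primary endpoint is feasibility and acceptability, and neither it nor any stated sample size depends on d. The correction should be made, but the trial does not turn on it.

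**What to change.** 1. In Section 11.1, replace four and eight months with 12 and 24 weeks. In Section 8.3, align the 10-week label with the 12-week assessment.
2. Take the arm difference at 12 and 24 weeks, with a 95% CI, from the mixed model in all randomised participants, adjusting for the HADS stratum. Either use the follow-up scores as outcomes with the baseline score as a covariate, or keep all time points as outcomes with a common baseline mean in both arms. State which.
3. As a clarification, name the SD that divides the difference. Report the baseline SD, the SD of change and the baseline/follow-up correlation, so that the full-scale trial can be sized with the SD that matches its analysis.
4. As a separate minor clarification, state the MEMS baseline period (a pre-randomisation one, if it exists for all participants), or report the MEMS effect size as the between-arm difference over the 24 weeks divided by its pooled between-participant SD.

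The cost is wording, a fuller statement of the secondary model and a few extra summaries. All the variables are already collected, and no visit, sample size or study procedure changes.

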11.2 Missing Data

The analyses for this study will focus on study completers to estimate the effect of the virtual, tailored intervention. The primary endpoint will be based on acceptability and feasibility aspects of the study. We will use the intention-to-treat principle for analyses with all randomized subjects. After we examine patterns of missingness, we will use maximum likelihood with multiple imputation to account for missing data.

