3.2 Inclusion & Exclusion Criteria

Eligibility criteria (Table 1) will maximize homogeneity, reflect study focus, enhance rigor, and consider limitations. The intervention targets adherence barriers identified in women, as male BCS face different challenges.⁴⁷ While patients with metastatic cancer are also treated with endocrine therapy, there are different facilitators and barriers to adherence with incurable disease. Therefore, the focus on early-stage BCS preserves the intervention scope. BCS with Ductal Carcinoma In Situ (DCIS) or Lobular Carcinoma In Situ (LCIS) will be eligible as they experience distress related to breast cancer and adherence challenges to AET as well. The recruitment window of 1 week to 36 months maximizes the likelihood that women have initiated AET and aims to improve adherence in the initial years that are most clinically beneficial.¹⁷ Up to 105 women will be enrolled to ensure that at least 4-5 participants complete the run-in period and that at least 60 participants will complete study participation. Participants who self-identify as part of a minority racial/ethnic population will be offered the opportunity to participate in a qualitative, semi-structured exit interview to explore patient feedback on the cultural awareness relevance of the STRIDE study, regardless of randomization. This interview will last approximately 15 minutes.

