(stridestudy.mgh.harvard.edu). The structure of each website post can be viewed in Appendix 30.25. The website will move into production after IRB approval. This is a website created with the support of IT at MGH/HMS and is viewable to those with the link to the website URL. The website will contain no advertisements or other content. It will only contain the relaxation file, and the individual sessions from the work book that the intervention participants receive, so that they can also have an electronic version accessible for the future. Study staff will provide instructions for participants to access this website via email as part of the intervention session reminders (Appendix 30.14). In addition to the overall study PI, [name], trained clinical psychology practicum students, clinical psychology fellows, licensed psychologists or social workers on the study team at MGH will deliver the intervention, to ensure successful administration of the intervention. Interventionists will complete a post-intervention survey for each group intervention, which will document process variables such as session length, session interventionist, and session attendance. [name] has ample experience delivering this type of intervention and was a protocol therapist on several NIH-funded CBT-based studies. She will conduct weekly clinical supervision with trained interventionists. 80% of sessions will be audio-recorded and at least 10% randomly selected, stratified by interventionist, and reviewed with [name] for treatment fidelity. Content fidelity will be assessed by calculating the percentage of key intervention topics addressed out of total topics, with a goal of 90%.⁵¹ Feedback will be given to interventionists to enhance adherence to the protocol.

Finally, participants who identify as part of a racial/ethnic minority population will be offered the opportunity to participate in a qualitative exit interview to provide feedback on the STRIDE program.

Medication Monitoring Control. Participants in the comparison condition will not receive the STRIDE intervention; however, they will monitor medication-taking with MEMS Caps and undergo standard care with oncology follow-up.

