10.0 Data and Specimen Banking: Not applicable

11.0 Data Management* and Confidentiality

11.1 Data Analysis

To determine feasibility in a pilot randomized controlled trial (N=100), estimate effect size, and finalize the intervention and study protocol to plan a full-scale, adequately powered efficacy trial.

Power calculation. The primary objective of this pilot study is to demonstrate feasibility, defined as (1) enrollment rate > 50%, (2) retention rate > 70%, and (3) attendance rate \geq 70% (i.e. \geq 70% of participants complete at least 4 of 6 sessions). At the time of the original protocol approval, we

estimated an accrual goal of 80 (75 in RCT and 5 in run-in phase) participants; therefore, the following power estimates are based on that number. We estimated that the enrollment rate will be 60%. If 134 patients are approached and 80 are enrolled, the lower limit for an exact, one-sided 95% confidence interval for the estimated enrollment rate will be 53%. Furthermore, we anticipate that the retention and attendance rates will both be 80%, and with 80 enrolled participants, the lower limit for an exact, one-sided 95% confidence interval for the retention and attendance rates will be 71%. Thus, based on our estimates of the feasibility parameters, the study will demonstrate feasibility of the adherence intervention. We have now expanded our accrual goal to 100 participants, which serves to only increase our power and rates of enrollment, retention, and attendance.

Primary Aim. To examine the feasibility and acceptability of a tailored, small-group, Telehealth intervention (STRIDE) compared to a medication monitoring control for survivors of breast cancer taking adjuvant endocrine therapy.

Hypothesis 1: The study will be feasible, defined by recruitment (enrollment rate > 50%), retention (completion rate of follow-up assessments > 70% of all participants who complete baseline) and attendance (attendance rate of at least 70% of participants completing at least 4 of 6 sessions [60%]).

Hypothesis 2: The study will be acceptable demonstrated by >75% of participants reporting average satisfaction scores greater than the scale's mid-point (Client Satisfaction Questionnaire).

Secondary Aim. To assess effects of the STRIDE intervention on adherence to AET, symptom distress, and satisfaction with AET.

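### Section 11.2 commits both to a completer analysis and to intention-to-treat for the intervention effect, ranks neither, and does not define a completer

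*Combined protocol and SAP*

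**What the plan says.** Section 11.2 (Missing Data) has four sentences. The first reads "The analyses for this study will focus on study completers to estimate the effect of the virtual, tailored intervention". The second says only that the primary endpoint concerns acceptability and feasibility. The third reads "We will use the intention-to-treat principle for analyses with all randomized subjects". The fourth says that, once patterns of missingness have been examined, "we will use maximum likelihood with multiple imputation to account for missing data".

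Section 11.1 plans mixed effects models on repeated measures for the secondary outcomes and a Cohen's d for change in each arm. It names no analysis set for either. It then uses the effect sizes in the power analysis for a full-scale trial.

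The word *completer* occurs only in section 11.2. Elsewhere, completion means different things:

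- Retention in section 11.1: "completion rate of follow-up assessments > 70% of all participants who complete baseline", with no time point given.
- Attendance in section 11.1: "attendance rate of at least 70% of participants completing at least 4 of 6 sessions".
- Accrual in section 3.2: enrolment is set so that "at least 60 participants will complete study participation".

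**The concern.** The first and third sentences of section 11.2 describe different analysis sets for the same quantity, the effect of the intervention. An analyst could follow either and be within the plan. The choice could also be made after the results are known.

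The two sets are not equally good. Comparing everyone as randomised keeps the groups comparable at baseline. Comparing completers conditions on something that happens after allocation and that the intervention itself may influence, so the women left in the two arms need not be alike.

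What is at stake is the set of secondary and exploratory effect sizes (adherence, symptom distress, satisfaction with therapy, and the psychosocial measures). Section 11.1 carries effect sizes forward to plan the efficacy trial. Section 4.0 gives better detection of group differences in secondary outcomes as a reason for raising RCT accrual from 75 to 100, so these comparisons are not incidental to the study.

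**Working it through.** **1. Is there a ranking anywhere?** In section 11.2, the first sentence ties completers to estimating the effect. The second concerns the primary endpoint and does not bear on the choice. The third and fourth concern all randomised women and missing data. None calls one analysis main and the other supportive. Section 11.1 says the longitudinal analyses use all time points, but that describes the model and not the women in it. There is no ranking.

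**2. The plan's own completion figure.** Section 11.1 states "we anticipate that the retention and attendance rates will both be 80" (per cent). It gives 71% as the lower limit of an exact one-sided 95% interval with 80 participants.

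- Inputs: x = 0.80 × 80 = 64, n = 80.
- Formula: lower limit = 5th percentile of Beta(x, n − x + 1) = Beta(64, 17).
- Result: 71.2%, which matches the stated 71%. The 80% is therefore the plan's working value.

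**3. Women set aside by a completer analysis.** Take the RCT size of 100 (section 4.0) and assume that a completer is a woman who is retained.

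- At the anticipated 80%: 100 × 0.80 = 80 kept, 20 set aside.
- At the 70% feasibility threshold: 100 × 0.70 = 70 kept, 30 set aside.

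Retention is defined on women who complete baseline. Randomisation is stratified on the baseline HADS (section 9.1), so applying the rate to those randomised is a reasonable approximation.

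**4. What the choice could do to the next trial (illustration only).** The documents give no effect size by completion status, so the values here are assumed. Suppose completers gain d and non-completers gain nothing, with completion the same in both arms. Then d for all randomised = completion proportion × d for completers. Per-arm size for 80% power at two-sided 5% with SD 1 is n = 2 × (1.960 + 0.842)² / d², rounded up.

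| d in completers | Completion | d in all randomised | n per arm from completer d | n per arm from all-randomised d |
|---|---|---|---|---|
| 0.5 | 80% | 0.40 | 63 | 99 |
| 0.5 | 70% | 0.35 | 63 | 129 |
| 0.3 | 80% | 0.24 | 175 | 273 |
| 0.3 | 70% | 0.21 | 175 | 356 |

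This is one scenario. If the control women doing worst were the ones to leave, the completer contrast would be too small instead. The table shows that the choice can matter, not which way it will go.

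**The case against.** The best defence is that section 11.2 leans towards intention-to-treat. It ends on everyone randomised and on imputation, which has little purpose in a completer analysis, and section 11.1 plans a mixed model over all time points. The completer sentence may simply be left over. That lowers the chance that it would be followed. It does not settle the matter, because the completer sentence is the only one of the four that mentions estimating the effect.

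The consequence is also limited. Section 11.1 says the pilot is not powered for group differences, and it checks the next trial's size against a clinically meaningful difference and the literature. With 50 per arm (equal split assumed), the 95% half-width for d is about 1.96 × √(2/50) = 0.39, larger than the 0.10 gap between 0.5 and 0.40 in the illustration. This stands as a limit on importance. It is no reason to leave two rules in place.

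Several stronger readings are tempting, and the documents do not support them:

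- **Selection in one arm only.** A reader might take completion to mean attending at least 4 of 6 sessions. Since "Participants in the comparison condition will not receive the STRIDE intervention", that would keep 40 of 50 in STRIDE at 80% attendance against all 50 controls. No section links *completer* to attendance, and the term appears under a missing-data heading. The nearest wording, in section 3.2, applies to both arms.
- **40 of 100 set aside.** A reader might subtract the section 3.2 floor of 60 from 100. But 60/75 = 80%, so the floor fits the former RCT goal of 75 at the same anticipated rate. It is not a forecast of 60% completion.
- **Cohen's d is a completer figure in any case.** This would follow only if d were computed without imputation, and section 11.2 plans imputation.
- **Late forms are dropped.** Section 9.3 expects some 12-week forms from intervention participants to be out of window, but nothing says they would be excluded.
- **The satisfaction criterion is compromised.** Its base could be stated more fully. That is missing detail, and any effect depends on assumed return rates.

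**Conclusion.** The point holds as a contradiction in the text. Section 11.2 gives two analysis sets for the intervention effect, ranks neither and leaves *completer* undefined. It should be fixed before analysis.

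Its reach is the secondary and exploratory between-arm effect sizes and their use in planning the efficacy trial. Following the completer sentence would set aside about 20 of 100 women, assuming that completion means retention and that retention is the anticipated 80%. A reader might infer that the effect would be overstated. The documents do not show that: neither the size nor the direction of any bias can be derived from them, and the per-arm sizes in the table rest on assumed effects. Enrolment, retention and attendance are defined separately and do not change, and no figure stated in the plan changes.

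**What to change.** In section 11.2, delete the completer sentence. State that the main set for the secondary and exploratory group comparisons is all randomised participants, analysed as assigned, with all available data in the mixed model already planned in section 11.1. State in section 11.1 that the effect sizes used to plan the efficacy trial come from that same set.

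If a completer analysis is still wanted, label it a sensitivity analysis and define *completer* in the same way for both arms. The definition must also work for MEMS, which is electronic monitoring over the whole 24 weeks and not a questionnaire.

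The cost is a few sentences, with no new data and no new model. The drawback is that the effect sizes may be less favourable than those in completers.
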